If safety data suggest increase benefit combined with increased harm for the 60 mg dose compared to the 45 mg dose, we will discuss potential options with the DSMB. For example we may see increased rate of re-arrest with the 60 mg dose, but a higher rate of survival to hospital admission or to discharge. In this case, an argument to use the 60 mg dose would be made.

Finally if both the 45 and 60 mg dose demonstrate an adverse safety signal then we will abandon plans for a phase 3 trial.

PHASE 2. EXAMINE THE SAFETY AND EFFICACY OF FIELD ADMINISTRATION OF SODIUM NITRITE DURING RESUSCITATION OF OUT-OF-HOSPITAL CARDIAC ARREST

The hemodynamic effects of the optimal dose of IV nitrite administered in patients with cardiac arrest are unknown. A significant negative hemodynamic effect from nitrite would decrease the proportion of patients admitted to the hospital, increase rate of re-arrest, or increase the need for vasopressor support in the field. In Seattle/King County, typically 40% of out-of-hospital cardiac arrest patients attended to by paramedics have ROSC and are admitted to the hospital. In this study, 1500 patients

with out-of-hospital cardiac arrest who are undergoing resuscitation by paramedics will be randomized to receive placebo (n=500) or 45 mg IV (n=500) or 60 mg dose (n=500) of sodium nitrite. We will have 80% power to detect an absolute increase in hospital admission rate of 8% (1-sided .05 level test for each of the two comparisons (45 mg vs placebo and 60 mg vs placebo, no adjustment for multiple comparisons), with a hospital admission rate of 40% in the placebo group and with one interim analysis and stopping only for potential futility and/or harm). We will examine the proportion of patients who survive to discharge as a secondary measure of efficacy.

Overview of Study design and definitions

In this phase 2 study, a total of 1500 patients with out-of-hospital cardiac arrest in Seattle/King County will be enrolled. This will be a randomized clinical trial and patients will receive either two different doses of IV sodium nitrite (45 mg or 60 mg) or placebo during resuscitation in the field by paramedics. The primary safety outcome will be proportion of patients surviving to hospital admission and primary efficacy outcome will be survival to discharge.

Patients will be eligible for both studies if:

1. Intravenous access/intraosseous access
2. Cardiac arrest, either VF or non-VF patients receiving ACLS by Seattle Medic One paramedics.

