The target population for randomization will be the 1000 treated cardiac arrest patients (per year) and thus we expect to enroll about 85% of the treated cardiac arrest patients (n=850/year) will meet eligibility requirements and be enrolled into the study. King County EMS providers have enrolled a similar proportion of eligible patients in the ongoing Resuscitation Outcomes Consortium (ROC) drug trial¹. We are allowing for enrollment to occur over 2.5 years.

Phase 2 (n=1500) Randomized clinical trial

This will be a randomized, placebo control study to determine safety and efficacy of sodium nitrite during resuscitation.

Randomization

Patients will be randomized to the 45 mg or 60 mg or placebo group on a 1:1:1 basis. Each paramedic unit will carry a study kit, which will be labeled with a study number. Each kit will contain a sterile sodium nitrite syringe or identical appearing placebo syringe (normal saline). The paramedic will place the content of the syringe into the IV line over 1-2 min. Once a study kit has been opened, the patient will be considered randomized, even if the paramedic is unable to administer the study drug.

Before enrollment commences, the study statistician will randomize each study kit number, to either nitrite 45, nitrite 60 mg, or placebo by masked allocation using permuted blocks of concealed size. This list will be given to the investigational pharmacy team at Harborview Medical Center and the numbered kits will be assembled with the properly assigned placebo or nitrite. Besides the study number all kits will look exactly the same. Once the paramedics have used the kit, a new kit will be placed into the paramedic unit. Only the investigational pharmacy staff and (Drs. [name] and [name], study statisticians) will know whether nitrite or placebo was administered. All other study staff (paramedics, nurses, investigators) will be blinded. There will be no facility for emergency unblinding. There are two clinical reasons for this decision. Firstly, knowledge of treatment assignment would not impact any care decisions being taken if an adverse event occurred. Secondly, there is no antidote to the study medication.

Intervention:

Treatment group: Randomized patients will receive 45 mg or 60 mg IV nitrite or placebo. Patients will receive the dose as soon as possible after CPR or defibrillation (if necessary), IV access is established and after first round of ACLS drugs have been delivered.

Preparation of nitrite doses:

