Unexpected Adverse Events (UAE) These will be defined as any serious unexpected adverse effect on health or safety or any unexpected life-threatening problem caused by, or associated with, a device, if that effect or problem was not previously identified in nature, severity, or degree of incidence in the investigation plan or application, or any other unexpected serious problem associated with a device that relates to the rights, safety or welfare of subjects. Death or neurological impairment will not be considered an adverse event in this study, as it is an expected part of the natural history of the illness for a large proportion of the population.

Covariates

Key covariates of interest include:

Initial rhythm- (i) VF, versus (ii) PEA, versus (iii) asystole, versus (iv) unknown.

Observational status of arrest: (i) witnessed by EMS, versus (ii) witnessed by bystanders, versus (iii) unwitnessed.

Bystander CPR status: (i) performed, versus (ii) not performed, versus (iii) unknown.

Response time interval from call to arrival at scene by EMS, among witnessed cardiac arrests: (i) < 10 minutes, versus (ii) \geq 10 minutes;¹⁰

Gender: (i) male versus (ii) female.

Time from cardiac arrest to awakening, death, or hospital discharge alive will be determined by review of hospital records. The place to which the patient is discharged and if it differs from where they lived before the cardiac arrest will be abstracted: home, rehabilitation, or some other supervised care setting. The degree of medical support and the timing of changes will be coded: full support; do not attempt resuscitation; and limitation or withdrawal of artificial life-sustaining treatments as indicated by “comfort care”.

Analyses for Phase 2 study

Baseline Factors and Covariates:

Recorded will be demographics, response times (call receipt to arrival at patient side, etc.), witnessed status, bystander CPR, location of arrest (public vs. private location), resuscitation therapies (drugs, shocks, advanced airway), presence of reactive pupils or spontaneous respirations, and first recorded ECG rhythm (VF or non-VF).

Also recorded will be major procedures after the index arrest (in-hospital cooling, coronary catheterization, percutaneous coronary intervention, other), withdrawal of care (DNAR status), restoration of spontaneous circulation, and potential adverse events

Analyses

1. Primary outcome:

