Statistical analyses for the phase 2 pilot study will be on an intention-to-treat basis. A one-sided test for proportions will be used to test the primary hypotheses separately for two comparisons: 45 mg versus placebo and 60 mg versus placebo. The primary hypotheses that will be tested (stated under the alternative): (1.1) The administration of 45 mg IV of sodium nitrite during resuscitation will increase the proportion of patients who survive until hospital admission.

(1.2) The administration of 60 mg IV of sodium nitrite during resuscitation will increase the proportion of patients who survive until hospital admission.

a) Primary outcome (survival to hospital admission)

1.1 H_0 : *The rate of survival to admission (π) is the same or worse in the 45 mg group vs the placebo arm or*

H_A *lower in the 45 mg group compared to the placebo group. H_0 : $\pi_{Placebo} \geq \pi_{45mg}$. H_A : $\pi_{Placebo} < \pi_{45mg}$*

1.2 H_0 : The rate of survival to admission (π) is the same or worse in the 60 mg group vs the placebo arm or

H_A lower in the 60 mg group compared to the placebo group: $H_0: \pi_{Placebo} \geq \pi_{60mg}$. $H_A: \pi_{Placebo} < \pi_{60mg}$

b) In secondary analyses we will adjust for the following predictors in generalized estimating equation models for binary outcomes to increase the efficiency: age, witnessed status, initial rhythm (VF vs non-VF), location (public vs. private), bystander CPR, response time (time from 911 call to arrival at the scene).

In the event that a patient is enrolled twice in the trial, all data pertaining to the second enrollment will be excluded from the analysis.

2. Secondary outcomes and exploratory analyses

Survival to hospital discharge, the number of ICU-free days in the first 28 days, survival at 24, 48 h, and neurologic status at time of discharge will be assessed and were chosen as additional markers of efficacy of sodium nitrite in improving outcomes.

The MRS at discharge will be used as a binary measure using the cut-points ≤ 3 vs. > 3 and as a continuous measure. Analyses of MRS will employ the similar techniques as for the primary outcome. No adjustment for multiple comparisons will be made since the secondary outcomes will be used to corroborate the conclusions from the primary outcome and not to draw final conclusions.

3. Safety Analysis

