Regarding the primary hypotheses: This study will have 80% power to detect an absolute increase in hospital admission rate of 8.0% (1-sided 0.05 level test, with a hospital admission rate of 40% in the placebo group) for each of the treatment arms (45 mg or 60 mg) when compared to placebo (without adjustment for multiple comparisons). We believe that not adjusting for multiple comparisons is justifiable for this early phase exploratory study, because the major Type I error is to discontinue any further investigation of a new treatment. Figure 1 provides sensitivity analyses to the power calculations by providing power estimates for a range of effect sizes and three rates of survival to hospital admission (30%, 40% and 50%) (applicable to each of the two primary comparisons). The study will be monitored by the DSMB at least four times, after about one quarter, about half and about three quarters of patients are enrolled and at the end of the study. Because of the size of the study, a single interim formal analysis will be performed (in addition to the final analysis). Of note, the DSMB can recommend stopping of the trial if there are concerns apparent at any of the reviews even if no formal interim analysis is scheduled. A one-sided boundary was chosen such that the study will only stop for futility and/or harm if the maximum likelihood estimate of the differences in proportions of survival to hospital admission is -0.001 or less (i.e. a slightly lower proportion of patients in the treatment arm survives to hospital admission than in the control arm after 500 patients have been enrolled). At the interim analysis no consideration will be made regarding stopping the study early for superiority.

[figure not shown]

Figure 1: Power for a study with 30%, 40% or 50% survival to hospital admission for effect sizes ranging from 6% to 10%.

Regarding the secondary hypothesis of survival to hospital discharge: The study will have more than 80% power to detect an absolute increase in survival to hospital discharge or 6.7% (1-sided 0.05 level test) in each of the two treatment groups with a survival to hospital discharge rate of 20% in the placebo group. Power estimates were obtained using SeqTrial (S-Plus).

Potential outcomes after safety analysis: (stopping rules)

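### The adjusted secondary model enters initial rhythm as VF versus non-VF; separate rhythm levels would use data already classified and gain a little precision at almost no cost

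*Combined protocol and SAP*

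**What the plan says.** The primary analysis uses no covariates: "A one-sided test for proportions will be used to test the primary hypotheses separately for two comparisons". Item b under Analyses, 1. Primary outcome, then adds a secondary analysis, a generalized estimating equation model for the binary outcome, with the stated aim of better efficiency. Besides age and witnessed status, it adjusts for "initial rhythm (VF vs non-VF), location (public vs. private), bystander CPR, response time (time from 911 call to arrival at the scene".

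Rhythm is described in three other places:

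- **Definitions** classifies the initial rhythm as asystole, VF, VT or PEA, with a separate criterion for each, and has the PEA rate recorded.
- **Covariates** names it as a key covariate with four levels: "Initial rhythm- (i) VF, versus (ii) PEA, versus (iii) asystole, versus (iv) unknown".
- **Baseline Factors and Covariates** lists the first recorded ECG rhythm as VF or non-VF.

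Response time also has more than one description. Covariates has "Response time interval from call to arrival at scene by EMS, among witnessed cardiac arrests", cut at 10 minutes. Baseline Factors and Covariates runs from call receipt to the patient's side, and the model runs from the 911 call to arrival at the scene. Neither of these two carries a restriction to witnessed arrests or a cut-point.

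**The concern.** Adjustment gains precision to the extent that the covariates explain the outcome. The plan defines PEA and asystole separately and calls four-level rhythm a key covariate, then merges PEA, asystole and unknown in the one model meant to use that information. If admission rates differ between PEA and asystole, the merged term leaves that difference in the residual variance.

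Pulseless VT is also left without a clear place. It is defined as an initial rhythm but does not appear in the four-level list, and a literal VF versus non-VF split puts it with asystole and PEA. The analyst would have to decide where it goes.

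What is at stake is a modest amount of precision, and one undocumented coding decision, in a secondary analysis.

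**Working it through.** **1. The plan's own figure.** Inputs: "placebo (n=500) or 45 mg IV (n=500) or 60 mg dose (n=500) of sodium nitrite" (Phase 2 introduction), and "This study will have 80% power to detect an absolute increase in hospital admission rate of 8.0" percent with a "1-sided 0.05 level test, with a hospital admission rate of 40% in the placebo group" (Sample Size and Monitoring plan). So n = 500 per arm, 40% versus 48%, one-sided 0.05.

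- Standard error under the null, pooled rate 0.44: √(2 × 0.44 × 0.56 / 500) = 0.03139.
- Standard error under the alternative: √((0.40 × 0.60 + 0.48 × 0.52) / 500) = 0.03129.
- Power = Φ[(0.08 − 1.645 × 0.03139) / 0.03129] = Φ(0.906) = 81.8%.

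The futility look (continue if the difference exceeds −0.001) brings this to 79.1% with the look at 167 per arm (500 enrolled in all), or 81.1% at 250 per arm. The stated 80% is reproduced. It belongs to the unadjusted test and does not depend on how any covariate is coded.

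**2. Cost of merging rhythm levels.** The documents give neither the rhythm mix nor admission by rhythm. The four sets below are assumptions, each averaging about 40% admission. Order: VF, PEA, asystole, unknown.

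| Set | Share (%) | Admission (%) | Overall (%) |
|---|---|---|---|
| A | 25, 25, 45, 5 | 60, 45, 27, 40 | 40.4 |
| B | 25, 25, 45, 5 | 60, 40, 30, 35 | 40.2 |
| C | 30, 25, 40, 5 | 60, 35, 30, 30 | 40.2 |
| D | 20, 30, 45, 5 | 65, 50, 22, 40 | 39.9 |

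Formulas, with s the level share, p the level admission rate and m the overall rate:

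- R² = Σ s(p − m)² / [m(1 − m)], once with four levels and once with the last three merged.
- Variance ratio = (1 − R² two-level) / (1 − R² four-level).
- Adjusted power: the formula in step 1 with n replaced by 500 / (1 − R²).

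Example, set A. Overall m = 0.404, so m(1 − m) = 0.2408. The four-level between-group variance is 0.01821, giving R² = 0.0756. Merging gives a non-VF rate of 0.3387 and a between-group variance of 0.01281, so R² = 0.0532. The variance ratio is 0.9468 / 0.9244 = 1.024. Effective n is 541 against 528 per arm.

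| Set | R² four-level | R² two-level | Variance ratio | Power four-level | Power two-level | Loss (points) |
|---|---|---|---|---|---|---|
| A | 0.0756 | 0.0532 | 1.024 | 84.4% | 83.6% | 0.8 |
| B | 0.0608 | 0.0541 | 1.007 | 83.8% | 83.6% | 0.2 |
| C | 0.0712 | 0.0695 | 1.002 | 84.2% | 84.1% | 0.1 |
| D | 0.1254 | 0.0657 | 1.068 | 86.1% | 84.0% | 2.1 |

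The loss is largest in set D, where PEA and asystole differ most (50% versus 22%). The two-level term still improves on no adjustment in every set (83.6% to 84.1% against 81.8%). These powers take rhythm as the only covariate and ignore the futility look. The effective-n step is a large-sample approximation, because the plan does not state the link function or the effect measure.

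**3. Cost of the change.** Four levels need three indicator terms and two levels need one, so there are two more parameters in a model for 1,500 patients.

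**4. Response time.** The model's own entry applies to every patient, because call and arrival times exist whether or not the arrest was witnessed. The Data Collection section takes response times from the paramedic form. The number of patients lost through the definition in the model is therefore zero.

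**The case against.** The strongest reply is that nothing here is an error. Baseline Factors and Covariates also lists rhythm as VF or non-VF, which matches the model. A coarser prespecified covariate causes no bias in a randomised trial with "Patients will be randomized to the 45 mg or 60 mg or placebo group on a 1:1:1 basis" and still gains over no adjustment. All of that stands, and it is why the point is only an improvement. It does not answer why the finer classification, which the Definitions already require, should go unused in a model added for efficiency.

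A reader might infer something stronger from the Covariates section: that response time exists only for witnessed arrests, so unwitnessed patients drop out and the adjusted model loses much of its power. The documents do not support this. The model carries its own unrestricted definition. The Covariates list is also not the model specification, since it includes gender, which the model omits, and lacks age and location, which the model includes. A power figure for a witnessed-only analysis would describe something the plan does not propose.

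For EMS-witnessed arrests, arrival may precede the arrest, so call-to-arrival time is not a delay to care. A baseline covariate need not be a causal delay, however, and witnessed status is already in the model. How to code the time for this group is a matter of preference.

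**Conclusion.** The point holds as a minor, free improvement to a secondary analysis. Two-level rhythm is a permitted but less efficient choice. Across the four assumed sets it makes residual variance 0.2% to 6.8% larger than four levels would, or about 0.1 to 2.1 points of power. The size rests on assumed rhythm shares and admission rates and on a large-sample approximation. It would be near zero if PEA and asystole had similar admission rates. Pulseless VT is not modelled in these figures; placing it is a matter of clarity.

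The differing response-time descriptions are a wording inconsistency, with no loss of patients under the model's definition. The primary test, the sample size and the stated 80% power are unaffected.

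**What to change.** In item b under Analyses, 1. Primary outcome, replace the two-level rhythm term with four levels: VF/VT, PEA, asystole and unknown. This gives pulseless VT an explicit place and keeps unknown as its own level. Use the same levels in Covariates and in Baseline Factors and Covariates.

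In the same edit, align the response-time wording in Covariates with the unrestricted definition used in the model.

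The cost is a few words and two model parameters. The rhythm classes are already defined in the protocol, so no new assessment is needed, and neither the sample size nor the primary analysis changes.

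### The primary test is valid but ignores six pre-dose covariates that the trial already collects; adjusting for them would be cheap and may add a few points of power, though the documents cannot say how many

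*Combined protocol and SAP*

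**What the plan says.** Under Analyses, item 1 (Primary outcome), each dose is compared with placebo by intention to treat: "A one-sided test for proportions will be used to test the primary hypotheses separately for two comparisons". No covariate enters.

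Item b) of the same section continues: "In secondary analyses we will adjust for the following predictors in generalized estimating equation models for binary outcomes to increase the efficiency". The predictors are age, witnessed status, initial rhythm (VF or not), public or private location, bystander CPR and response time. No link function, effect measure or clustering unit is given.

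The Randomization section describes "masked allocation using permuted blocks of concealed size" at 1:1:1 and names no stratification factor. The section on baseline factors and covariates shows that all six items are recorded, with age under demographics. The Intervention section places the study dose after CPR or defibrillation, IV access and the first round of ACLS drugs.

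The sample-size section claims "80% power to detect an absolute increase in hospital admission rate of 8.0" percentage points, "with a hospital admission rate of 40% in the placebo group". The design paragraph gives the level as "1-sided .05 level test for each of the two comparisons". One formal interim look, after 500 patients, stops for futility or harm if "the maximum likelihood estimate of the differences in proportions of survival to hospital admission is -0.001 or less".

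**The concern.** The plan recognises that adjustment improves efficiency, yet leaves it out of the two comparisons that test the primary hypotheses. As described, randomization does not balance on these factors either, so neither design nor primary analysis uses them.

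The six covariates are safe to adjust for. They describe the patient, the arrest or the EMS response, they are settled before the syringe is given, and they are recorded by blinded staff.

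At stake is precision for the same 8-point difference at the same sample size. Adjustment would also reduce, though not remove, the effect of chance imbalance in the measured covariates. Power has little margin: under one reading of the interim timing it falls just below 80%.

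The secondary model does not fully fill the gap. Without a stated link and summary measure, its result may be a conditional odds ratio, whereas the hypotheses, the 8-point target and the interim boundary are all stated in proportions.

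**Working it through.** **Inputs from the plan.** 500 patients per arm; 40% survival to admission on placebo and 48% on nitrite; one-sided 0.05 for each dose; no multiplicity adjustment; one interim look with boundary -0.001 after 500 patients. That number means about 167 per arm if it counts all three arms, or 250 per arm if it counts one comparison.

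**Input not in the plan.** R-squared, the share of outcome variance explained by the six covariates. The documents give no value, so 0 to 0.15 is assumed.

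**Step 1: reproduce the stated power, unadjusted.**

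- SE = sqrt((0.40×0.60 + 0.48×0.52)/500) = sqrt((0.24 + 0.2496)/500) = 0.0313.
- Fixed-design power = Φ(0.08/0.0313 − 1.645) = 81.9%. The pooled-variance version gives 81.8%.
- With the look, power is the probability that the interim difference exceeds -0.001 and the final z exceeds 1.645. The two statistics have correlation sqrt(n_interim/500). The normal approximation gives 79.2% at 167 per arm and 81.3% at 250 per arm. Simulation of patient-level outcomes gives 79.7% and 81.7%.
- Type I error of the unadjusted test with the look is 4.6% (167 per arm) or 4.9% (250 per arm).

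The plan's 80% is reproduced and the test is valid.

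**Step 2: effect of adjustment by formula, fixed design.** Adjustment multiplies the variance by (1 − R²). Power = Φ(0.08/(0.0313×sqrt(1 − R²)) − 1.645) and effective n = 500/(1 − R²). The smallest difference with 80% power is (1.645 + 0.842)×0.0313×sqrt(1 − R²).

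| Assumed R² | Effective n per arm | Power | Smallest difference, 80% power |
|---|---|---|---|
| 0 | 500 | 81.9% | 7.8 points |
| 0.02 | 510 | 82.6% | 7.7 points |
| 0.05 | 526 | 83.6% | 7.6 points |
| 0.10 | 556 | 85.3% | 7.4 points |
| 0.15 | 588 | 87.0% | 7.2 points |

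The formula ignores the cost of fitting six covariates and the interim look, so it is an upper guide.

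**Step 3: simulation with both included.** There were 40,000 trials per case, with a Monte Carlo error of about 0.2 point for power. The six covariates were two continuous and four binary with prevalences 25%, 50%, 20% and 50%, and effects were scaled to the stated R²; all of these are assumed. The adjusted test was a logistic model standardised to the risk difference, with an influence-function standard error and a degrees-of-freedom correction. The interim rule stayed on the unadjusted difference. Entries are power, unadjusted to adjusted.

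| Assumed R² | No look | Look at 167 per arm | Look at 250 per arm |
|---|---|---|---|
| 0 | 82.1 to 81.6% | 79.7 to 79.1% | 81.5 to 81.0% |
| 0.02 | 82.1 to 82.2% | 79.5 to 79.5% | 81.5 to 81.5% |
| 0.05 | 82.4 to 83.6% | 79.9 to 80.9% | 81.8 to 82.9% |
| 0.10 | 82.4 to 85.4% | 79.8 to 82.2% | 81.8 to 84.4% |
| 0.15 | 82.3 to 86.7% | 79.6 to 83.3% | 81.7 to 85.6% |

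Type I error of the adjusted test, with 40% in both arms, is 5.0–5.2% without a look, 4.7–4.8% with the look at 167 per arm and 4.9–5.1% at 250 per arm. A separate simulation with different assumed covariate effects, no look and 4,000 runs per case agrees: power rises from 82.2% to 85.4% at an R² of 0.11.

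**The case against.** Nothing in the primary analysis is wrong. The test is valid, the promised power is met, and adjustment for the same six covariates on the same outcome is already planned. An unadjusted primary test backed by a pre-specified adjusted analysis is a legitimate choice. If the secondary model uses a logit link, it already captures the precision: the logistic Wald test and the standardised risk difference had the same power to within 0.2 point in simulation.

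The gain cannot be established from the documents and could be slightly negative. Chance imbalance is also limited at this size. For a binary covariate with 20% to 50% prevalence, the between-arm difference has a standard deviation of sqrt(2×0.2×0.8/500) = 2.5 points to sqrt(2×0.5×0.5/500) = 3.2 points. Finally, the study is described as exploratory, its dose choice for phase 3 rests mainly on safety, and no decision is shown to turn on 0 to 4 points of power.

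All of this is fair, and it rules out calling the point an error. It does not remove the asymmetry: a worst-case loss of about 0.5 point against a gain of 1 to 4 points if the investigators' chosen predictors are even moderately prognostic. The precision in a secondary analysis does not help the comparison that decides the primary hypotheses. The open link, effect measure and coding also need settling wherever the adjusted analysis sits.

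**Conclusion.** The point holds as a recommended improvement, not as a defect that must be corrected. The unadjusted test is valid and has about 80% to 82% power under either reading of the interim timing. With that look included, adjustment changes power by about -0.5 point if the covariates carry no information, by nothing at an R² of 0.02, and by about +1 to +4 points at 0.05 to 0.15.

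These figures rest on an assumed R² range, assumed covariate prevalences and effects, complete outcome data and an unadjusted interim rule. Confidence is medium, because the true prognostic strength of the six covariates is not documented.

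**What to change.** Make the primary comparison of each dose with placebo a covariate-adjusted binary regression using the six listed predictors. Standardise it to the marginal risk difference, with a robust standard error, at one-sided 0.05. This keeps the 8-point target on its present scale. Retain the unadjusted test as supportive.

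State the following before unblinding:

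1. How response time is defined for all patients, including EMS-witnessed arrests. The Covariates section categorises it only as "Response time interval from call to arrival at scene by EMS, among witnessed cardiac arrests".
2. Where an unknown initial rhythm, allowed in the Covariates section, falls in the VF versus non-VF predictor.
3. An unknown level for every categorical covariate, including witnessed status and location.
4. A simple imputation blind to arm, such as the overall median, for missing age or response time.
5. That the interim boundary of -0.001 stays on the unadjusted difference in proportions.

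Two loose ends can be tidied at the same time. The Covariates section lists gender as key but the adjustment list omits it, and the clustering unit of the generalized estimating equations is not given.

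The cost is some added SAP text and modelling, plus about 0.5 point of power if the covariates prove uninformative. No additional patients or data are needed.
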